- Wedge-shaped and segmental or lobar consolidation
- Air crescent sign
- Cavity.

For other pulmonary mold disease, a reverse halo sign is also included.

OR

Allogeneic BMT / HSCT or neutropenic participants who have non-specific focal infiltrates, confirmed by CT scan (or HRCT) or MRI, and have mycological evidence of disease will also be classified as probable. The presence of non-specific focal infiltrates or evidence of disease on plain chest X-ray must be confirmed by CT scan (or HRCT) or MRI within the 7 days after the first administration of study medication.

Non-Lower Respiratory Tract Disease (NLRTD)

See [Table 9](#) below for a summary of status of invasive fungal disease at baseline for participants with NLRTD.

Sino-Nasal Infection:

- CT scan or MRI showing sinusitis **PLUS** at least one of the following:
 - Acute localized pain (including pain radiating to eye)
 - Nasal ulcer, black eschar
 - Extension from the paranasal sinus bony barriers, including into the orbit.

Central Nervous System Infection:

- At least one of the following:
 - Focal lesions on imaging, or
 - Meningeal enhancement on CT or MRI.

c. MYCOLOGICAL CRITERIA:

(cytology, direct microscopy, culture from non-sterile sites, antigen detection)

- Either sputum, bronchoalveolar lavage (BAL), bronchial brush samples, or sinus cavity specimen demonstrating the presence of fungal elements either by culture of a mold (eg, *Aspergillus* species) or detection by cytology or direct microscopy of hyphal forms
- Or for Aspergillosis specifically, GM antigen detected in plasma, serum, BAL, or CSF at least one of the following positive results is an acceptable mycological evidence for

enrollment as probable IFD, and it is recommended to refer to the guideline of EORTC/MSG (version 2019) or EORTC/MSG ICU (version 2021)^{34, 35}:

- Single serum or plasma: ≥ 1.0 ;
- BAL fluid: ≥ 1.0
- Single serum or plasma: ≥ 0.7 and BAL fluid ≥ 0.8
- two consecutive values of either serum, plasma or BAL fluid between ≥ 0.5 to <1.0 (from two separate specimens of the same category)
- CSF: ≥ 1.0
- Or for *Aspergillus* species specifically, *Aspergillus* PCR at least one of the following:
 - plasma, serum, or whole blood 2 or more consecutive PCR tests positive
 - BAL fluid 2 or more duplicate PCR tests positive
 - At least 1 PCR test positive in plasma, serum, or whole blood and 1 PCR test positive in BAL fluid

Possible Invasive Fungal Disease

PLUS	At least one host factor [a] as above

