	At least one clinical feature [b] as above

NOTE: Participants fulfilling the criteria for possible IFD as defined above will be eligible for enrollment; however, confirmatory CT scan, GM test, **in addition to**, acceptable mycological criteria as defined above is required within the 7 days after the first administration of study medication.

BAL PCR (only): two or more duplicate PCR tests positive (2 or more aliquots of the same sample) are allowed to enroll as probable IFD. Specimens for culture and histology/cytology must be obtained from the BAL during the same procedure and serum GM must still be obtained per protocol requirements.

Table 8. Status of Invasive Fungal Disease at Day 7 for Participants with Lower Respiratory Tract Disease (LRTD)

Host Factors	Clinical Features "Lower Respiratory Tract Disease"	Mycological Criteria			
		No positive culture		Positive culture or microscopy (cytology/histology) of hyphal forms	
		Serum testing negative for GM ²	Serum/plasma testing positive for GM ² or Positive BAL GM ²	Nonsterile site (i.e. sputum, BAL, or bronchial brushing specimen)	Sterile site (i.e. transbronchial biopsy or open lung biopsy) or with associated tissue damage
Neutropenia (ANC < 0.5 x 10 ⁹ /L [<500/mm ³]) temporally related to the onset of fungal disease OR hematologic malignancy OR Receipt of an allogeneic hematopoietic stem cell transplant OR Receipt of a solid organ transplant OR prolonged use of corticosteroids (excluding among patients with allergic bronchopulmonary aspergillosis) at a therapeutic dose of ≥0.3mg/kg corticosteroids for ≥ 3 weeks in the past 60 days. OR treatment with other recognized T-cell immunosuppressants (such as calcineurin inhibitors, tumor necrosis factors-α blockers, lymphocyte-	Presence of at least one imaging sign on CT scan (or HRCT) or MRI: - Dense, well-circumscribed lesion (s) with or without a halo sign - Wedge-shaped infiltrate and segmental or lobar consolidation - Air crescent sign - Cavity OR Presence of new "nonspecific" imaging findings on CT scan (or HRCT) or MRI ¹ OR For other pulmonary mold disease, a reverse halo sign is also included	Possible	Probable		Proven

Table 8. Status of Invasive Fungal Disease at Day 7 for Participants with Lower Respiratory Tract Disease (LRTD)

Host Factors	Clinical Features "Lower Respiratory Tract Disease"	Mycological Criteria			
		No positive culture		Positive culture or microscopy (cytology/histology) of hyphal forms	

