4. ANALYSIS SETS (POPULATIONS FOR ANALYSIS)

Data for all participants will be assessed to determine if participants meet the criteria for inclusion in each analysis population prior to unblinding and releasing the database and classifications will be documented per standard operating procedures (SOP).

Population	Description	Applicable Analysis (for additional information refer to section 6)
Enrolled	"Enrolled" means a participant's, or their legally authorized representative's, agreement to participate in a clinical study following completion of the informed consent process and assignment to study intervention. A participant will be considered enrolled if the informed consent is not withdrawn prior to participating in any study activity after screening. Potential participants who are screened for the purpose of determining eligibility for the study, but do not	

Population	Description	Applicable Analysis (for additional information refer to section 6)
	participate in the study, are not considered enrolled, unless otherwise specified by the protocol.	
Intent-to-Treat (ITT)	The ITT population consists of all enrolled participants who receive at least 1 dose of study intervention. The ITT is the primary efficacy population.	Key secondary endpoint, main analysis (Section 6.2.1.1) Secondary analyses and sensitivity/supplementary/subgroup analyses (Sections 6.2.1.2 - 6.2.2) Baseline and other summaries and analyses (Section 6.5)
Modified Intent-to-Treat (mITT)	The mITT population consists of ITT participants who had proven or probable IFD as determined by the investigators based on the definition specified in protocol Appendix 9, Section 10.9.	Key secondary endpoint, supplementary analysis (Section 6.2.1.2) Secondary analyses (Sections 6.2.2-6.2.4) Baseline and other summaries and analyses (Section 6.5)
Mycological Intent-to-Treat IA (myITT-IA)	The myITT-IA population consists of mITT participants with proven or probable IA based on cytology, histology, culture, or GM and assessed by the investigators.	Key secondary endpoint, supplementary analysis (Section 6.2.1.2) Secondary analyses (Sections 6.2.2-6.2.4) Baseline and other summaries and analyses (Section 6.5)
Mycological Intent-to-Treat IM (myITT-IM)	The myITT-IM population consists of mITT participants with proven or probable IM based on cytology, histology, culture, or GM and assessed by the investigators.	Exploratory analysis (Sections 6.3.1-6.3.3) Baseline and other summaries and analyses (Section 6.5)

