6.5.8. Baseline IFD Characteristics

The assessment of IFD at baseline will be summarized as described in the following subsections. The summaries will be performed for mITT, myITT-IA, and myITT-IM populations. Baseline IFD characteristics is defined as the test obtained prior to the first dose and up to 7 days after the first administration of study medication.

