6.5.8.1. Mycological Assessments

Mycological assessments at baseline will be summarized by number and percentage of participants in the following categories:

- Histopathology /Culture evidence of IFD
- Single serum or plasma: ≥ 0.7 to < 1.0 and bronchoalveolar lavage (BAL) GM ≥ 0.8
- Single serum or plasma: ≥ 1.0
- BAL GM: ≥ 1.0
- Two consecutive values of either serum, plasma or BAL fluid between ≥ 0.5 to < 1.0 (from two separate specimens of the same category)
- No mycological evidence available.

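### The myITT-IA evidence list omits the Aspergillus PCR that Appendix 9 accepts for probable disease, and the baseline IFD tables do not fit the sets they are run on

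*SAP*

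**What the plan says.** **Analysis sets (SAP 4; same wording in Protocol 9.2).** ITT is every enrolled participant who received a dose, and is the primary efficacy population. mITT is the part of ITT with proven or probable IFD as judged by the investigator under Protocol Appendix 9. Within mITT, "The myITT-IA population consists of mITT participants with proven or probable IA based on cytology, histology, culture, or GM and assessed by the investigators". The mucormycosis set uses the same list: "The myITT-IM population consists of mITT participants with proven or probable IM based on cytology, histology, culture, or GM and assessed by the investigators".

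**Diagnostic criteria (Protocol Appendix 9, Section 10.9).** For Aspergillus, PCR is one of the accepted mycological criteria. One of the qualifying patterns is "At least 1 PCR test positive in plasma, serum, or whole blood and 1 PCR test positive in BAL fluid". A separate note covers BAL PCR on its own: "two or more duplicate PCR tests positive (2 or more aliquots of the same sample) are allowed to enroll as probable IFD". GM is tied to one disease: "Or for Aspergillosis specifically, GM antigen detected in plasma, serum, BAL, or CSF".

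**Baseline IFD tables (SAP 6.5.8).** "The summaries will be performed for mITT, myITT-IA, and myITT-IM populations". ITT is added only for signs and symptoms (6.5.8.5), where the IFD items are also to be listed. The mycology table (6.5.8.1) has one row for histopathology or culture, four GM rows, and "No mycological evidence available". The categorisation table (6.5.8.4) has six rows: proven and probable IM, proven and probable IA, Possible, and No IFD. In SAP 4, however, the ITT entry points to Section 6.5 as a whole.

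**The concern.** Appendix 9 decides who has probable disease. The myITT-IA definition then applies a second, shorter list of evidence and gives no reason for the difference. SAP 2.1 records no modification, and the protocol carries the same wording. Read literally, a participant who meets the protocol's own definition of probable IA on PCR alone is removed from the IA-specific set by type of test.

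That set carries the supplementary Day 42 and Day 84 mortality analyses (SAP 6.2.1.2, 6.2.2). It is also one of only two sets named for every secondary response endpoint (SAP 6.2.3, 6.2.4).

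The baseline tables raise a related problem. Possible IFD is deliberately enrolled (Protocol 4.2.2), so diagnostic certainty is a main descriptor of the ITT population. Under the specific text of 6.5.8, the table that shows certainty is not run on ITT.

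**Working it through.** The plan has no figure of its own on this point. Its only sizing figure, 86.6% in Protocol 9.5, reproduces (1 − 0.97^66 = 0.866) and does not depend on anything below. The check is mainly a comparison of texts.

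**1. A PCR-only participant with a host factor and a clinical feature**

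| Source | Classification |
|---|---|
| Appendix 9, mycological criteria and BAL PCR note | Probable |
| mITT (refers to Appendix 9) | Included |
| myITT-IA (cytology, histology, culture or GM) | Not included |
| Appendix 9 Table 8 (no positive culture, serum GM negative) | Possible |

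The first three rows give the mismatch. The fourth shows that Appendix 9 disagrees with itself: Table 8 has no PCR column. If Table 8 governed, the same participant would leave mITT as well, so the conflict reaches both sets.

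**2. GM in myITT-IM.** Membership first requires proven or probable IM. Appendix 9 bases that diagnosis on histopathology or growth, and Tables 8 and 9 mark GM as applying to Aspergillus only. The word therefore admits nobody if Appendix 9 is followed.

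**3. Rows against sets in SAP 6.5.8.** mITT requires proven or probable IFD, and both myITT sets lie inside it. In 6.5.8.4 the Possible and No IFD rows, 2 of 6, are therefore zero by definition in all three sets. Proven or probable disease from another mould is allowed in mITT but has no row. In 6.5.8.1 there is no row for PCR or for CSF GM, both of which Appendix 9 accepts. The only row left for such a participant is the one for no mycological evidence, although the SAP states no rule that puts them there.

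**4. What can be recovered.** Crude mortality is reported as number and percentage on ITT and again on mITT. Subtracting gives the participants outside proven or probable IFD and their counted deaths. It does not separate Possible from No IFD. If 20%, 40% or 60% of 66 treated participants were Possible (assumed shares), that is 66 × 0.2 = 13, 66 × 0.4 = 26 or 66 × 0.6 = 40 participants.

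**5. Size of the exclusion (illustration only).** Assume n proven or probable IA cases, PCR-only included, with 20% mortality, close to the 19% that Protocol 2.2.4 reports for isavuconazole in the pivotal trial. Removing k PCR-only participants from d deaths in n gives d/(n − k) if all k survived and (d − k)/(n − k) if all k died.

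| n | d | k | All k survived | All k died |
|---|---|---|---|---|
| 30 | 6 | 1 | 6/29 = 20.7% | 5/29 = 17.2% |
| 30 | 6 | 3 | 6/27 = 22.2% | 3/27 = 11.1% |
| 50 | 10 | 1 | 10/49 = 20.4% | 9/49 = 18.4% |
| 50 | 10 | 3 | 10/47 = 21.3% | 7/47 = 14.9% |

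One exclusion moves the rate by at most 20.0 − 17.2 = 2.8 points at n = 30 and 20.0 − 18.4 = 1.6 points at n = 50. The exact 95% intervals before any exclusion are 7.7% to 38.6% (6/30) and 10.0% to 33.7% (10/50).

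**The case against.** The strongest defence is that a mycological subset may legitimately require conventional evidence. PCR-only participants stay in ITT and mITT, and every response analysis is also run on mITT. Such participants may be few: after BAL PCR, culture and histology/cytology specimens and serum GM must still be obtained, and the schedule's mycology row names tissue nucleic acid only. One exclusion moves a rate by far less than the width of its interval. All of this stands and limits the importance of the point. It does not explain the shorter list, because neither document says PCR was left out on purpose.

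Four stronger readings are tempting, and the documents do not support them.

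- A reader might infer that the weight of possible IFD in the ITT mortality cannot be seen. The combined group outside proven or probable IFD, and its deaths, follow from ITT minus mITT. Only the split is missing from the tables, and categorisation is listed.
- A reader might infer that ITT is plainly excluded from the baseline IFD tables. SAP 4 assigns ITT to all of Section 6.5, so this is a conflict within the SAP. The Possible and No IFD rows make sense if ITT was meant.
- A reader might infer that GM lets aspergillosis cases into myITT-IM. It does not, for the reason in step 2.
- A reader might infer that other moulds are invisible. Primary diagnosis type (IA, IM, other) is summarised on ITT under SAP 3.4 and 6.5.1, and 6.5.8.2 has mould rows. What is missing is diagnostic certainty for that group.

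**Conclusion.** The point holds as a mismatch between stated rules, with limited consequences. The myITT-IA list omits a criterion that the criteria text of Appendix 9 accepts. Table 8 conflicts with that text. SAP 4 and SAP 6.5.8 disagree on ITT, and the two tables lack rows for participants whom the plan admits.

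The effect on results cannot be sized from the documents, which give no expected number of IA or PCR-only participants. The figure of about 2 to 3 points per exclusion rests on an assumed 30 to 50 IA cases and 20% mortality. It affects a supplementary mortality analysis and one of the two sets used for the secondary response rates. The primary safety analysis and the ITT analysis of the key secondary endpoint do not change. The change is worth making because set membership should be settled before the data are seen.

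**What to change.** 1. In Protocol 9.2 and SAP 4, define myITT-IA as mITT participants with proven or probable IA by any Appendix 9 mycological criterion, including PCR. If PCR is meant to be excluded, say so and give the reason.
2. Reconcile Table 8 with the criteria text of Appendix 9 on PCR-only cases, so that mITT membership is unambiguous.
3. State in SAP 6.5.8 that 6.5.8.1 to 6.5.8.4 are run on ITT as well, in line with SAP 4.
4. Add PCR and CSF GM rows to 6.5.8.1, and rows for proven and probable other mould to 6.5.8.4.
5. Delete GM from the myITT-IM list as a tidy-up. It changes no one's membership.

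The cost is revised set definitions in both documents, a correction to Table 8, a few table rows and one extra column. No visit, sample or sample-size change follows, provided that PCR results used for categorisation are already recorded. Settle it before database lock, and before the interim snapshot if that has not been taken, because SAP 7.2 includes the supplementary mortality analyses.

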5. GENERAL METHODOLOGY AND CONVENTIONS

All data analyses will be performed according to this pre-specified analysis plan. Any deviations from this plan will be documented in the clinical study report. All computations will be performed prior to rounding. The boundaries of 2-sided 95% confidence intervals (CI) will be rounded to 3 decimal places.

5.1. Hypotheses and Decision Rules

No formal statistical hypothesis testing will be conducted for efficacy analysis.

5.2. General Methods

5.2.1. Analyses for Binary and Categorical Endpoints

Binary and categorical data will be summarized by number and percentage of participants within the category.

For all-cause mortality and crude rate, the 95% CIs for the rates will be calculated based on the exact binomial distribution.

5.2.2. Analyses for Continuous Endpoints

Continuous endpoints will be summarized descriptively including number of participants (n), mean, standard deviation (SD), median, minimum and maximum.

5.2.3. Analyses for Time-to-Event Endpoints

A survival analysis of all-cause mortality will be conducted using the Kaplan-Meier (K-M) method and estimated survival curves will be displayed graphically when appropriate. Number and percent of participants who experienced the event as well as number and percent of participants who were at risk will be reported. The survival rates will be estimated using the K-M method by Day 42, and Day 84 based on ITT, mITT, and myITT-IA populations; and be estimated by Day 42, Day 84, Day 120, and Day 180 based on myITT-IM populations. The cumulative probabilities of mortality rates (100%-survival rates) will then be calculated. For 95% CI, Greenwood's method will be used to estimate the standard error for the survival rates; the 95% CI will first be constructed for the log-log transformed survival rates ie. $L(t) = \log(-\log(S(t)))$; and antilogging the lower and upper bounds of this CI ie. $S(t) = \exp(-\exp(L(t)))$ will be performed to get the 95% CI for survival rates in right range; the 95% CI for the mortality rate will be calculated by 100% - survival rates 95% CI boundaries.

5.3. Methods to Manage Missing Data

Any missing data were presented as part of a missing category except for those situations described as follows. For calculation of crude mortality, a participant with the last known survival status is before evaluation visit (i.e., Day 42, Day 84) or missing and the last assessment day is on or before the visit (i.e., Day 42, Day 84) will be treated as death. When change from baseline to a postbaseline value was calculated, only participants with baseline and at least one postbaseline value will be included in the calculation. In the time-to-event analysis, a participant without a reported death will be censored on the participant's last known alive day which will be the latest of randomization day, last study assessment day, latest study drug treatment day, date with follow-up therapies, date with AEs, last contact day, last PK sampling day, or date of discontinuation. For example, if a participant's last survival status is before day 42 and this participant's last known alive day is after Day 42, say day 50, then this participant will be censored on day 50.

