8.2.5. Mycological Assessment of Invasive Fungal Infection

All mycological assessments will be based on results generated in the local laboratory to assess the participant's eligibility at screening and following mycological response. Pathogen isolates must be shipped to the central reference laboratory for confirmation of local mycological results.

Baseline mycological assessment (Screening through Day 7) of the participant's IFD status will be performed according to the microbiological manual or the best local practice using local laboratories, including obtaining suitable samples for fungal culture and isolation and/or biopsy/biological fluid samples from the infected site for histology/cytology. Day 42 and Day 84 assessments will be performed within ± 7 days, as well as Day 126 and Day 168 for IM participants. EOT assessments will be performed within ± 3 days.

Baseline and different (species level) pathogen isolates (defined as clinically significant isolates) will be stored and shipped to a central laboratory for isolation of fungal species and susceptibility testing.

If the identities of the pathogens differ between the central and local laboratories, the central laboratory results will take precedence over the local results for both eligibility and response evaluation purposes.

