8.2.7. Survival Status

Survival status will be recorded until the Follow-up visit and be evaluated through EOT in all participants, irrespective of when treatment was discontinued. Detailed requirement should be performed as specified in [Section 1.3 SoA](#).

If the participant has died, the date and cause of death along with the reporting of SAE details will be recorded in the eCRF.

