9.3.1. Efficacy Analyse

No formal statistical hypothesis testing will be conducted for efficacy analyses.

The key secondary efficacy endpoint of crude rate of all-cause mortality through Day 42 will be analyzed on the ITT population. Any death that occurs after first dose of study intervention through Day 42 will be included. A participant with the last known survival status before Day 42 or missing and the last assessment day before Day 42 will be treated as death. The 95% CI of the crude mortality rate will be calculated based on an exact binomial distribution.

The same analysis will be repeated for the mITT, myITT-IA, and myITT-IM populations.

All-cause mortality rate over time by Day 42 will also be estimated using the KM method. In the KM analysis, time to death will be observed until Day 84 for participants with IA and Day 180 for participants with IM.

The other secondary endpoint of the percentage of all-cause mortality through Day 84 will be summarized and analyzed similarly to the all-cause mortality through day 42.

The clinical, mycological, radiological, and overall response at EOT, Day 42 and Day 84 will be summarized. The 95% CIs of the response rates will be calculated based on an exact binomial distribution.

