6.2. Secondary Endpoint(s)

6.2.1. Percentage of All-cause Mortality on Day 42 (Key Secondary Endpoint)

6.2.1.1. Main Analysis

- Estimand strategy: Treatment (Section 2.2.2).
- Analysis set: ITT population (Section 4). Any death that occurs after first dose of study drug through Day 42 will be included.
- Analysis methodology: The crude mortality rate will be summarized by number and percentage of participants through Day 42. The 2-sided 95% CIs for crude rate will be

calculated based on a binomial distribution. Any death that occurred after first dose of study drug through Day 42 will be included. A participant with the last known survival status is before Day 42 or missing and the last assessment day is before Day 42 will be treated as death.

- Intercurrent events and missing data: All data collected (after prohibited medication or after discontinuation of treatment) will be included. Missing data will be handled as described in Section 5.3.

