6.2.1.3. Subgroup Analysis

If data permits, subgroup analyses of all-cause mortality on Day 42 will be performed based on the ITT population for the following subgroups:

- Age category 1: (≤ 45 , > 45 to ≤ 65 , > 65)
- Age category 2: (≤ 65 , > 65 to ≤ 75 , > 75)
- Gender (Male, Female)
- BMI category: (< 25 , ≥ 25 to < 30 , ≥ 30)
- eGFR category: < 60 , ≥ 60
- Baseline Neutropenic Status: Yes/No

6.2.2. Percentage of All-cause Mortality on Day 84

Percentage of all-cause mortality on Day 84 will be summarized and analyzed using the same approach as described in Sections 6.2.1.1-6.2.1.3.

6.2.3. The Crude Rate of Overall Response at EOT, Day 42, and Day 84

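### The rule that scores missing survival status as death is worded two ways, and read as calendar days it can count a survivor seen on time on Days 77-83 as a Day 84 death

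*SAP*

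**What the plan says.** **Wording of the rule.** SAP 5.3 sets the crude-mortality rule for both time points. Its first condition is that the last known survival status precedes the evaluation visit or is missing. Its second condition and result read "the last assessment day is on or before the visit (i.e., Day 42, Day 84) will be treated as death". SAP 6.2.1.1, the main analysis of the key secondary endpoint, ends its rule differently: "the last assessment day is before Day 42 will be treated as death". Protocol 9.3.1 agrees with 6.2.1.1: "or missing and the last assessment day before Day 42 will be treated as death".

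**Which wording applies.** SAP 6.2.1.1 also sends missing data to 5.3. SAP 6.2.2 says Day 84 mortality "will be summarized and analyzed using the same approach as described in Sections 6.2.1.1-6.2.1.3". Both wordings therefore reach both time points.

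**Contacts.** The Schedule of Activities gives the Day 42 and Day 84 visits a window of ±7 days. Protocol 8.2.5 repeats it for mycology ("Day 42 and Day 84 assessments will be performed within" ±7 days). Follow-up is 4 weeks ±7 days after the last dose and, under Protocol 4.1, may fall before or after Day 84. Participants withdrawn from treatment or failing before Day 42 are telephoned for survival status at Days 42 and 84 (Schedule of Activities, footnote k). SAP Appendix 3 defines analysis windows for response and safety data but none for survival status.

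**The concern.** A programmer cannot follow both wordings. For a participant last assessed on Day 42 or Day 84 itself, with survival status earlier or missing, one section gives a death and the other does not.

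The second difficulty arises under either wording. Scoring an unknown outcome as death is a recognised conservative choice, but a participant reached alive on Day 80, inside the permitted window, is not an unknown outcome in the ordinary sense. If that was the last contact, both conditions are met and the participant enters the Day 84 numerator. A clinical assessment made on the same Day 80 visit would count as a Day 84 response assessment, because Appendix 3 maps Days 50-91 to Day 84.

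At stake is an upward bias in crude Day 84 mortality that depends on visit scheduling, in a single-arm study with no comparator to share it. The planned interim report has mortality as its only efficacy analysis. With about 28 participants, each false death there adds 1/28 = 3.6 points.

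**Working it through.** **Denominator.** The plan expects 66 treated participants, and the ITT set is everyone dosed. Its one sample-size figure reproduces: 1 − 0.97^66 = 0.866, the stated 86.6%. This confirms the 66 but has no bearing on the rule.

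**The rule as logic.** Let V be 42 or 84, S the day of last survival status and A the last assessment day. The sentence does not show how its *or* and *and* group; I read it as follows.

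- SAP 5.3: death if (S < V or S missing) and A ≤ V.
- SAP 6.2.1.1 and Protocol 9.3.1: death if (S < V or S missing) and A < V.

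Applied at V = 84 to participants with no reported death:

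| Last survival status | Last assessment | SAP 5.3 | SAP 6.2.1.1 |
|---|---|---|---|
| Day 77, 80 or 83 | same day | death | death |
| Day 84 or 88 | same day | not death | not death |
| missing | Day 84 | death | not death |
| Day 80 | Day 84 | death | not death |
| Day 112 (Follow-up) | Day 112 | not death | not death |

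Rows 3 and 4 show the conflict between wordings. Row 1 shows the false death common to both.

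**Who is exposed at Day 84.** If the last dose is on Day L, Follow-up falls between L + 21 and L + 35.

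- L = 48: Days 69-83. Follow-up always precedes Day 84 for last doses up to Day 48.
- L = 49: Days 70-84. L = 62: Days 83-97. For last doses on Days 49-62, Follow-up may precede Day 84.
- L = 63: Days 84-98. From here Follow-up, if attended, is on or after Day 84 and removes the problem.

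Participants with mucormycosis have status collected on Days 126, 168 and 180 (footnote k), so they are largely protected.

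**Size.** Each misclassified survivor adds 1/66 = 1.5 points. The documents give no distribution of treatment duration or contact days, so the rest is illustration. Assume 13, 16 or 20 true deaths by Day 84 (19.7%, 24.2%, 30.3%), that 20% of survivors have Day 84 as their last contact, and that contacts are uniform over the 15 days 77-91, so that 7/15 fall before Day 84.

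- 13 deaths: 53 × 0.20 × 7/15 = 4.9 false deaths, +7.5 points.
- 16 deaths: 50 × 0.20 × 7/15 = 4.7, +7.1 points.
- 20 deaths: 46 × 0.20 × 7/15 = 4.3, +6.5 points.

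With 16 true deaths and 5 false ones, 16/66 = 24.2% (exact 95% CI 14.5-36.4) becomes 21/66 = 31.8% (20.9-44.4). At a 40% share the same formula gives about 9-10 false deaths (+13 to +15 points). At a share of zero there are none.

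**The case against.** **The visit reading.** The strongest reply is that SAP 5.3 speaks of status before the evaluation visit, and Day 84 is also a visit label. If the Day 84 visit takes place on Day 80, status comes from that visit and not from before it, so nothing is imputed. This reading is available, and it means the text does not establish that compliant survivors will be scored dead. But 6.2.1.1 and Protocol 9.3.1 say Day 42 without mentioning a visit, and the worked example in 5.3 ("then this participant will be censored on day 50") uses calendar days. The ambiguity stands.

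**Importance.** Day 84 mortality is a descriptive, non-key secondary endpoint in a study with a safety primary and no hypothesis test. The bias runs against the drug. A Kaplan-Meier analysis to Day 84, which censors such participants, is already planned. All this is true and limits the severity. It does not tell a programmer which rule to use.

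**Stronger readings the documents do not support.**

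- A reader might infer that the key Day 42 endpoint is equally affected. An early Day 42 contact is normally followed by the Day 84 contact, so it is much less exposed.
- A reader might take Protocol 8.2.7 ("Survival status will be recorded until the Follow-up visit and be evaluated through EOT in all participants") to end survival collection at Follow-up. Its next sentence defers to the Schedule of Activities, and Protocol 7.1 also requires Day 42 and Day 84 status.
- The crude and Kaplan-Meier rules do use different alive dates, so one participant could be a Day 42 death in one and censored on Day 50 in the other. That needs a later date that is neither an assessment nor a survival status, so it is minor.
- A reader might object to the discontinuation date in the last-known-alive list. The documents do not say how it is set for lost participants, and it affects only Kaplan-Meier censoring.
- The ±7 days is stated for visits. Nothing says how telephone calls spread around Day 84, so the uniform spread is purely an assumption.

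**Conclusion.** Two defects hold. First, SAP 5.3 conflicts with SAP 6.2.1.1 and Protocol 9.3.1 for the same crude mortality analyses. On the grouping used here, the result changes only when the last assessment is exactly on Day 42 or Day 84 and survival status is earlier or missing. Second, on the calendar-day reading, either wording turns a survivor last contacted on Days 77-83 into a Day 84 death. The exposed group is mainly participants without mucormycosis: certainly those whose last dose is by Day 48, possibly those on Days 49-62.

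The cost is 1.5 points per participant, with a total that cannot be derived from the documents. The 4-5 false deaths above rest on an assumed 20% share and uniform contact days; larger totals need larger assumed shares and should not be presented as expected. This should be fixed, but it does not threaten the primary safety objective.

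**What to change.** Put one rule in SAP 5.3, SAP 6.2.1.1 and Protocol 9.3.1:

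1. Impute death only when there is no evidence of being alive on or after Day 42 or Day 84. Evidence is a survival status, an assessment or a dated contact, as in the last-known-alive definition the SAP already uses for Kaplan-Meier.
2. Count an alive contact inside the Day 42 or Day 84 visit window as alive for that time point, and add a survival-status window to SAP Appendix 3.
3. Report observed and imputed deaths on separate lines.

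The cost is a small change to SAP wording and programming, and a matching clarification in Protocol 9.3.1. No visits are added. The trade-off is that a death between an in-window contact and Day 84 is counted only if it is reported.
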